4.3.2.2 Supportive secondary endpoints

4.3.2.3 Effect

Endpoint title	Time frame	Unit
Change in bone age	From baseline (week 0) to visit 8 (week 52)	Years
Change in height SDS	From baseline (week 0) to visit 6 (week 26)	-10 to +10
Change in Height velocity SDS	From baseline (week 0) to visit 6 (week 26)	-10 to +10

Protocol
Trial ID: NN8640-4245
UTN: U1111-1207-9741
Eudract Number: 2018-000232-10~~CONFIDENTIAL~~Date:
Version:
Status:
Page:12 June 2020
7.0
Final
21 of 102**Novo Nordisk**

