7.8 Treatment after the end of the trial

When discontinuing trial products, either at the scheduled end of treatment visit or if trial product is discontinued, the subject should be transferred to a suitable marketed product according to local treatment guidance at the discretion of the investigator.

If a subject discontinues trial product during the trial and is transferred to a marketed product this should be recorded as ancillary therapy according to Section [7.7.1](#).

Protocol
Trial ID: NN8640-4245
UTN: U1111-1207-9741
EudraCT Number: 2018-000232-10

~~CONFIDENTIAL~~

Date:
Version:
Status:
Page:

12 June 2020
7.0
Final
36 of 102

Novo Nordisk

8 Discontinuation/Withdrawal criteria

The subject may be discontinued at any time during the trial at the discretion of the investigator.

Efforts must be made to have the subjects, who discontinue trial product, attend the planned visit schedule until visit 8. Only subjects who withdraw consent will be considered as withdrawn from the trial. Subjects must be educated about the continued scientific importance of their data, even if they discontinue trial product.

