8.1 Discontinuation of trial treatment

A subject who does not fulfil the eligibility criteria (inclusion/exclusion criteria) must not be randomised. Randomisation in violation of any of the eligibility criteria is a GCP non-compliance and must be reported to the sponsor without delay. This will be handled as an important protocol deviation, and the independent ethics committee(IEC)/institutional review board (IRB) and regulatory authorities must be notified according to local requirements. If there are no safety concerns, trial treatment may be continued or resumed at the discretion of the investigator after agreement with the sponsor's global medical expert.

The subject must be discontinued from trial product, if the following applies:

- Pregnancy
- Intention of becoming pregnant
- Simultaneous participation in another clinical trial of an approved or non-approved IMP
- Tumour development
-

See the flowchart [2](#) for data to be collected at the time of treatment discontinuation and follow-up and for any further evaluations that need to be completed.

The purpose of the follow-up visit is to collect information about AEs.

For convenience of the subject the follow up visit can be performed as a telephone contact. The follow up visit should be performed as a site visit for subjects with an ongoing injection site reaction at visit 24. If pregnancy is suspected the subject must come to the site for the follow up visit where a pregnancy test is performed.

The primary reason for discontinuation of trial product must be specified in the end-of-treatment-form in the case report form (CRF), and final drug accountability must be performed. A treatment discontinuation session must be made in the IWRS.

Protocol
Trial ID: NN8640-4245
UTN: U1111-1207-9741
Eudract Number: 2018-000232-10~~CONFIDENTIAL~~Date:
Version:
Status:
Page:12 June 2020
7.0
Final
37 of 102**Novo Nordisk****Treatment discontinuation prior to visit 8**

If a subject discontinues treatment prior to visit 8, visit 24A should be performed at least 7 days after the last dose of trial product and prior to starting treatment with a marketed product. The follow up should be performed a minimum of 30 days after the last dose of trial product.

Although the treatment has been discontinued, the subject should continue to follow the planned visit 5, 6, 7 and 8. If subject or family refuses to attend the planned visit schedule, then the first coming visit 6 or 8 is of most importance to attend.

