After treatment discontinuation (visit 24A) only the following assessments are required:

- Height
- IGF-1
- AEs
- Concomitant medication

- **Treatment discontinuation at or after visit 8**
- If a subject discontinues treatment at or after visit 8, visit 24A should be performed at least 7 days after the last dose of trial product and prior to starting treatment with a marketed product. The follow up should be performed a minimum of 30 days after the last dose of trial product and the subject should then be withdrawn from the trial.

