10.2 Definition of analysis sets

The Full analysis set (FAS) is defined as all randomised subjects exposed to the trial product. Exclusion of data from analyses should be used restrictively, and normally no data should be excluded from the FAS. The subjects or observations to be excluded, and the reasons for their exclusion must be documented before database lock (DBL). The subjects and observations excluded from analysis sets, and the reason for this, will be described in the CTR. Subjects will be analysed “as treated”.

The Safety analysis set (SAS) is defined as all randomised subjects exposed to trial product. Subjects will be analysed “as treated”.

The Per Protocol (PP) analysis set is defined as subjects from FAS who have not violated any inclusion/exclusion criteria and have used the randomised treatment for at least 22 weeks (for subjects receiving somapacitan) or 154 days (for subjects receiving Norditropin®). Subjects will be analysed “as treated”.

All efficacy endpoints will be analysed using FAS and all safety endpoints will be analysed using SAS.

Protocol
Trial ID: NN8640-4245
UTN: U1111-1207-9741
EudraCT Number: 2018-000232-10~~CONFIDENTIAL~~Date:
Version:
Status:
Page:12 June 2020
7.0
Final
50 of 102**Novo Nordisk**

Two observation periods are defined,

- on-treatment: from first administration and up until last trial contact, visit 6 or 14 days after last administration, whichever comes first
- in-trial: from first administration and up until visit 6 or last trial contact, whichever comes first

The observation periods for the extension I part of the trial are defined analogously by exchanging “visit 6” in the definitions above with “Follow-up visit 25” for subjects who do not continue in extension II or “visit 8” for subjects continuing in extension II.

For the on-treatment observation period of the extension II part of the trial, “visit 6” in the on-treatment observation period definition above is exchanged with visit 24 or visit 24A for subjects who do not attend visit 24. The in-trial observation period for the extension II part of the trial is defined analogously by exchanging “visit 6” in the definition above with “Follow-up visit 25”.

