10.3.2 Secondary endpoints

Confirmatory secondary endpoints

NA

Supportive secondary endpoints

Main period:

Effect

Endpoint title	Time frame	Unit
Change in height SDS	From baseline (week 0) to visit 6 (week 26)	-10 to +10
Change in HV SDS	From baseline (week 0) to visit 6 (week 26)	-10 to +10

Pharmacodynamics

Endpoint title	Time frame	Unit
Change in IGF-I SDS	From baseline (week 0) to visit 6 (week 26)	-10 to +10
Change in IGFBP-3 SDS	From baseline (week 0) to visit 6 (week 26)	-10 to +10

Protocol
Trial ID: NN8640-4245
UTN: U1111-1207-9741
EudraCT Number: 2018-000232-10~~CONFIDENTIAL~~Date:
Version:
Status:
Page:12 June 2020
7.0
Final
52 of 102**Novo Nordisk**

The analysis of change in HV SDS, change in height SDS and change in bone age is based on FAS and the ‘in-trial’ observation period. The analysis of change in IGF-I SDS and change in IGFBP-3 SDS is based on FAS and the ‘on-treatment’ observation period.

Height SDS will be derived using Centres for Disease Control and Prevention (CDC) standards²⁴ and HV SDS will be derived using Prader standards²⁵ as reference data.

The secondary endpoints: change in height SDS, HV SDS, IGF-I SDS and IGFBP-3 SDS from baseline will be analysed using MMRM on available assessments from planned visits with baseline assessment as covariate and treatment, age group, sex, region and sex by age group interaction term as factors, all nested within week as a factor. An unstructured covariance matrix will be used to describe the variability for the repeated measurements for a subject.

Extension I period:

Endpoint title	Time frame	Unit
Change in bone age	From baseline (week 0) to visit 8 (week 52)	Years

Bone age will be analysed using an ANCOVA model on change from baseline in bone age/chronological age assessed at week 52 and the model will include treatment, age group, sex, region and sex by age group interaction term as factors and baseline bone age/chronological age as a covariate. The treatment difference estimate will be reported with corresponding 95% CI and p-value. Subjects without post-randomisation data for the analysed endpoint will not be included in the analysis.

Supportive secondary safety endpoints

Endpoint title	Time frame	Unit
Change in fasting plasma glucose	From screening (visit 1) to visit 6 (week 26)	mmol/l
Change in HOMA	From screening (visit 1) to visit 6 (week 26)	%
Change in HbA1c	From screening (visit 1) to visit 6 (week 26)	% point

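### For children who stop treatment before visit 8, the extension I in-trial period can close at follow-up visit 25, before the week-39 and week-52 heights that section 8.1 still asks for

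*Combined protocol and SAP*

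**What the plan says.** Section 10.2 defines the main-period in-trial window as "in-trial: from first administration and up until visit 6 or last trial contact, whichever comes first". For extension I it keeps that rule but replaces the named visit, "exchanging “visit 6” in the definitions above with “Follow-up visit 25” for subjects who do not continue in extension II"; for children who do continue, the named visit is visit 8.

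The opening of section 8 states: "Efforts must be made to have the subjects, who discontinue trial product, attend the planned visit schedule until visit 8". Section 8.1 then covers a child who stops trial product before visit 8. Visit 24A comes at least 7 days after the last dose. The follow-up visit comes next: "The follow up should be performed a minimum of 30 days after the last dose of trial product". In addition, "the subject should continue to follow the planned visit 5, 6, 7 and 8". On content, section 8.1 says "After treatment discontinuation (visit 24A) only the following assessments are required", and lists height, IGF-I, adverse events and concomitant medication. Footnote e of Table 2 confirms that the follow-up visit applies after visit 24A.

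On the analysis side, section 10.3.1 uses data from children who discontinued before week 26 in the primary analysis. Section 10.3.2 says "The analysis of change in HV SDS, change in height SDS and change in bone age is based on FAS" and the in-trial period. Section 10.3.5 extends the HV, height SDS and HV SDS models to week 52 but names no observation period.

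**The concern.** A child who stops trial product before visit 8 does not go on to extension II, so the visit that closes the extension I in-trial period is visit 25. For this child visit 25 need not be the last visit: it can come 30 days after the last dose, with visits 7 and 8 still ahead. Because the earlier of the two limits applies, the window closes at visit 25, and heights measured later fall outside the period whose purpose is to keep off-treatment data.

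This would make the handling of discontinuation differ between time points without the plan saying so. At week 26, heights after discontinuation count. At weeks 39 and 52 the same kind of height could be excluded by a definition for which no reason is given, although section 10.2 itself says that data should normally not be excluded from the FAS. Children would be asked to attend visits whose heights are then not used. The loss would be selective, because it touches only children who stopped.

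**Working it through.** The plan gives no figure on this point, so the check is one of timing.

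**Inputs**
- Follow-up visit 25: at least 30 days after the last dose, no upper limit stated (section 8.1).
- Visit 8 = week 52 (section 4.3.2.3).
- Visit 7 = week 39: an inference from the week-39 HV in section 10.3.1, because the week rows of the flowchart are blacked out.
- In-trial end = the earlier of visit 25 and last trial contact (section 10.2).

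**Cut-off by week of stopping, visit 25 at day 30**

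30 days / 7 = 4.29 weeks, so visit 25 falls at stop week + 4.29.
- Week-52 height is outside if stop week < 52 − 4.29 = 47.7.
- Week-39 height is outside if stop week < 39 − 4.29 = 34.7.

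| Stop week | Visit 25 at week | Week 39 | Week 52 |
|---|---|---|---|
| 20 | 24.3 | outside | outside |
| 30 | 34.3 | outside | outside |
| 38 | 42.3 | inside | outside |
| 48 | 52.3 | inside | inside |

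If the same window governs the four-visit HV model of section 10.3.5, its week-26 value is also outside for stops before 26 − 4.29 = 21.7, although that height is used in the primary analysis.

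**Sensitivity to a later visit 25**

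Assume stop times spread evenly over the period (my assumption; the documents give no distribution). For a lag of L days, the share of stops before week 39 with visit 25 ahead of visit 7 is (39 − L/7)/39. The share of stops before week 52 with visit 25 ahead of visit 8 is (52 − L/7)/52.
- L = 30: 89% and 92%.
- L = 60: 78% and 84%.
- L = 90: 67% and 75%.

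So the conflict does not depend on visit 25 falling exactly on day 30. It disappears only if visit 25 is held after visit 8.

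**Which results are exposed**
- Week-26 primary analysis and week-26 height SDS and HV SDS: the main-period window ends at visit 6 or last contact, so they are unaffected.
- Bone age at week 52: assigned to in-trial, but no X-ray is required after visit 24A, so little is lost.
- IGF-I SDS and IGFBP-3 SDS (section 10.3.2) and adverse events (section 10.3.5): analysed on-treatment, so the in-trial cut-off does not bear on them.
- Week-52 HV, height SDS and HV SDS (section 10.3.5): exposed, if they follow the in-trial period as their week-26 counterparts do.

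**Precision, for scale only**

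With the sample-size inputs of section 10.1 (n = 11 per arm, SD 2.6, difference 3.25 cm/year), a two-sample t-test with 20 degrees of freedom gives 79.6% power, matching the stated 80%. On the same basis the half-width of a pairwise 95% CI is t(0.975, 2n − 2) × 2.6 × √(2/n):
- n = 11: 2.31 cm/year.
- n = 10: 2.44 cm/year.

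This assumes that the SD also holds at week 52 and that one value is lost in each arm. It ignores what the repeated-measures model recovers from earlier visits.

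**The case against.** The strongest reply is that visit 25 need not come early. Thirty days is a minimum, Table 2 marks end of trial in the follow-up column, and section 8.1 withdraws a child after follow-up only when treatment stops at or after visit 8. A site could hold visit 25 after visit 8 without breaking the text, and any timing in the blacked-out flowchart row cannot be seen. Nor does section 10.3.5 say that its models use the in-trial period. Its SDS models run on available assessments from planned visits, and section 8.1 describes visits 5 to 8 as planned for these children.

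This stands in part. It makes the point conditional on when visit 25 is held and on which period applies at week 52. It does not remove the conflict: nothing requires visit 25 to wait for visit 8, and no sentence overrides the cut-off in section 10.2.

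A reader might infer more than the documents support:
- **A biased treatment comparison of known size or direction.** One child in an arm of 12 (60/5) whose 52-week HV is 1 to 3 cm/year lower would shift a raw mean by 1/12 to 3/12, or 0.08 to 0.25 cm/year. No source gives that deficit. Section 7.8 has children who stop transferred to a marketed product. A 52-week HV is cumulative from baseline: a child who stops at week 40 has 12/52 = 0.23 year left, so a 3 cm/year deficit would need slowing of 3/0.23 = 13 cm/year. The planned model also uses earlier visits, so the result is not a raw-mean shift.
- **A count taken from the 60-to-55 allowance in section 10.1.** That allowance concerns children not available at week 26, in a passage about withdrawal. A withdrawn child has no later visits to cut.
- **An in-trial period that adds 30 days to on-treatment.** On-treatment already extends 14 days after the last dose, so with visit 25 at day 30 the difference is 30 − 14 = 16 days.

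**Conclusion.** The conflict between sections 8.1 and 10.2 is real and should be corrected, but its reach is limited. Read literally, and with visit 25 at about day 30, attended week-39 heights are outside the extension I in-trial period for stops before about week 34.7, and week-52 heights for stops before about week 47.7. That is at odds with the use of post-discontinuation data at week 26.

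The conclusion rests on two conditions: visit 25 is held before visits 7 and 8, which section 8.1 allows but does not require; and the section 10.3.5 models use the in-trial period, which is inferred from the week-26 analyses. Only supportive week-52 results are at risk, and the documents do not support extending the concern to the primary comparison. They also do not allow an estimate of how many children would be affected, or of the size or direction of any bias.

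**What to change.** In section 10.2, for subjects who stop trial product before visit 8 and remain in the trial, end the extension I in-trial period at the later of visit 8 and follow-up visit 25, or at last trial contact if that comes first. Taking the later of the two matters. A cut-off at visit 8 alone would drop the follow-up contact of late stoppers: a stop at week 50 puts visit 25 at 50 + 4.3 = week 54.3 or later.

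In section 10.3.5, state that the week-52 HV, height SDS and HV SDS models use the FAS and this in-trial period.

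The cost is protocol or SAP wording. No visit or measurement is added, since section 8.1 already asks for the visits and the heights. The change should be made before the week-52 data are analysed.

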10.3 Statistical analyses

Biostatistics, Novo Nordisk, will be responsible for the statistical analyses.

All statistical tests will be conducted as two sided tests on the 5% significance level, unless stated otherwise. Age group is defined as a factor with 2 levels: < 6 years, \geq 6 years and region as a factor with 2 levels: Japan, rest of the world. No adjustment for multiple testing will be applied for this exploratory phase 2 trial.

10.3.1 Primary endpoint

Endpoint title	Time frame	Unit
HV	From baseline (week 0) to visit 6 (week 26)	cm/year

Height is measured at baseline and 26 weeks and the primary endpoint is derived as:

$HV = (\text{height at 26 weeks visit} - \text{height at baseline}) / (\text{time from baseline to 26 weeks visit in years})$.

Annualised HV at 13 weeks, 39 weeks and 52 weeks will be derived analogously to the primary endpoint : $(\text{height at } d \text{ weeks visit} - \text{height at baseline}) / (\text{time from baseline to } d \text{ weeks visit in years})$, where $d=13,39,52$.

The primary objective is to evaluate the effect of somapacitan vs Norditropin® on longitudinal growth in children with short stature born SGA with no catch-up growth by 2 years of age or older and the primary analysis of the primary endpoint is the main tool for achieving this. Conclusions from the primary analysis will be based on CIs for the specified treatment differences and not on hypothesis testing.

Protocol
Trial ID: NN8640-4245
UTN: U1111-1207-9741
EudraCT Number: 2018-000232-10

~~CONFIDENTIAL~~

Date:
Version:
Status:
Page:

12 June 2020
7.0
Final
51 of 102

Novo Nordisk

The primary analysis of the primary endpoint is based on FAS and the 'in-trial' observation period.

Annualised HV at 13 and 26 weeks will be analysed using a mixed model for repeated measurements (MMRM) with treatment, age group, sex, region and sex by age group interaction term as factors and height at baseline as a covariate, all nested within week as a factor. An unstructured covariance matrix will be used to describe variability for the repeated measurements for a subject. From the model the treatment differences at week 26: somapacitan 0.24 mg/kg/week vs Norditropin® CCI █ mg/kg/day, somapacitan 0.20 mg/kg/week vs Norditropin® CCI █ mg/kg/day, somapacitan 0.20 mg/kg/week vs Norditropin® CCI █ mg/kg/day, and somapacitan 0.16 mg/kg/week vs Norditropin® CCI █ mg/kg/day will be estimated with the corresponding 95% CI. Subjects without post-randomisation HV data will not be included in the primary analysis. Data from subjects who have discontinued randomised treatment before week 26 will be used in the primary analysis.

The analysis will be repeated on the PP analysis set as a sensitivity analysis.

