6.1 Inclusion criteria

Subjects are eligible to be included in the trial only if all of the following criteria apply:

- - 1. Informed consent of parent or legally acceptable representative of subject and child assent, as age-appropriate must be obtained before any trial-related activities.
 - a) The parent or legally acceptable representative of the child must sign and date the Informed Consent Form (according to local requirements).
 - b) The child must sign and date the Child Assent Form or provide oral assent (if required according to local requirements).
 - 2. Pre-pubertal children:
 - a) Boys:
 - Age \geq 2 years and 26 weeks and $<$ 11.0 years at screening.
 - Testes volume $<$ 4 ml.
 - b) Girls:
 - Age \geq 2 years and 26 weeks and $<$ 10.0 years at screening.
 - Tanner stage 1 for breast development (no palpable glandular breast tissue).
 - 3. Born small for gestational age (birth length and/or weight $<$ -2 SDS) (according to national standards).
 - **For Israel and Japan:** see [Appendix 9](#)
 - 4. Impaired height defined as at least 2.5 standard deviations below the mean height for chronological age and gender at screening according to the standards of Centers for Disease Control and Prevention.
For India: see [Appendix 9](#)
 - 5. Impaired height velocity defined as annualised height velocity below the 50th percentile for chronological age and gender according to the standards of Prader calculated over a time span of minimum 6 months and maximum 18 months prior to screening.
 - 6. No prior exposure to growth hormone therapy or IGF-I treatment.
 - 7. Gestational age at birth \geq 32 weeks.

Protocol
Trial ID: NN8640-4245
UTN: U1111-1207-9741
EudraCT Number: 2018-000232-10

~~CONFIDENTIAL~~

Date:
Version:
Status:
Page:

12 June 2020
7.0
Final
27 of 102

Novo Nordisk

8. Body Mass Index <95th percentile according to Centers for Disease Control and Prevention, Body Mass Index-for-age growth charts.

For India: see [Appendix 9](#)

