9.1.1 Body measurements

Body measurements will be assessed according to the flowchart [2](#).

Height

For height measurements, European Medicines Agency (EMA) guideline^{[20](#)} should be followed. A manual for height measurement prepared by Novo Nordisk A/S will be provided to the sites.

Standing height should be measured

- by a trained person blinded to treatment allocation (preferably the same person throughout the trial)
- preferably by using the same stadiometer
- at the same time (\pm 2 hours, compare to baseline-visit 2)

Protocol
Trial ID: NN8640-4245
UTN: U1111-1207-9741
Eudract Number: 2018-000232-10

~~CONFIDENTIAL~~

Date:
Version:
Status:
Page:

12 June 2020
7.0
Final
40 of 102

Novo Nordisk

- without shoes
- with 3 consecutive measurements
- in centimetres with one decimal to the nearest 1 mm or in inches with one decimal
-

Confirmation that height measurements have been performed by a trained person blinded to treatment allocation should be documented.

Body weight

Body weight will be measured in kilos (kg) or pounds (lb) with one decimal without shoes and wearing only light clothing.

Body weight should be measured preferably at the same time of the day and by using the same scale throughout the trial, if possible.

Body Mass Index

Body Mass Index will be calculated at the screening visit (Visit 1) using the CRF.

Body composition

Body composition will be measured using bioelectrical impedance analysis (BIA) including assessments such as muscle, fat and bone parameters.

Instructions will be provided to the sites describing procedures for body composition measurement.

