9.4 Safety assessments

Planned time points for all safety assessments are provided in the flowchart Section [2](#).

A **concomitant illness** is any illness that is present at the start of the trial (i.e. at the first visit) or found as a result of a screening procedure or other trial procedures performed before exposure to trial product.

Medical history is a medical event that the subject has experienced in the past.

In case of an abnormal and clinically significant finding, the investigator must record the finding on the Medical History/Concomitant Illness form if it is present at screening. Any new finding fulfilling the AE definition (see [Appendix 4](#)) during the trial and any clinically significant worsening from baseline (Visit 2) must be reported as an AE (see Section [9.2](#)).

Information related to children with short stature born SGA with insufficient catch-up growth

- Birth related information
- Height data
 - Standing height measured minimum 6 and maximum 18 months prior to screening in order to assess inclusion criterion 5. Standing height should be reported in centimetres with one decimal to the nearest 1 mm or in inches with one decimal. The pre-trial height assessment is collected to be used when evaluating inclusion criteria 5 and for baseline HV derivation.
 - Parental height: Standing height for both biological parents in centimetres with one decimal to the nearest 1 mm or in inches with one decimal.
- GH status, if available
 - Type of GH stimulation test and result of peak GH values.

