10.3.5 Other analyses

Annualized HV at 13 weeks, 26 weeks, 39 weeks and 52 weeks will be analysed using a MMRM with treatment, age group, sex, region and sex by age group interaction term as factors and height at baseline as a covariate, all nested within week as a factor. An unstructured covariance matrix will be used to describe the variability for the repeated measurements for a subject. From the MMRM the treatment differences at week 52 weeks will be estimated for the same treatment contrasts as for the primary analysis of the primary endpoint.

Height profiles will be presented by subject with time point for treatment switch in the extension II period (if applicable) and start of puberty (if applicable) indicated in the graphs. Annualised HV for the second year in trial will be derived as: (height at 104 weeks visit – height at 52 weeks visit) / (time from 52 weeks visit to 104 weeks visit in years). Annualised HV for the second year in trial will be analysed using descriptive statistics by treatment arm (treatment arm from main trial period), as well as by extension II period treatment arm. Annualised HV for third, fourth and fifth year in trial will be derived analogously and analysed using descriptive statistics.

Change in height SDS, HV SDS, IGF-I SDS and IGFBP-3 SDS from baseline to week 52 will be analysed using an MMRM on available assessments from planned visits similar to the MMRM used for the analysis of week 26 data, with baseline assessment as covariate and treatment, age group, sex, region and sex by age group interaction term as factors, all nested within week as a factor.

IGF-I SDS and IGFBP-3 SDS data from extension II will be analysed using descriptive statistics.

Protocol
Trial ID: NN8640-4245
UTN: U1111-1207-9741
EudraCT Number: 2018-000232-10~~CONFIDENTIAL~~Date:
Version:
Status:
Page:12 June 2020
7.0
Final
54 of 102**Novo Nordisk**

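### Optional low-cost improvement, not an error: the cm/year height velocity models adjust for baseline height but not for baseline height velocity, which the plan has to derive anyway

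*Combined protocol and SAP*

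**What the plan says.** Section 10.3.1 analyses annualised HV at weeks 13 and 26 by MMRM "with treatment, age group, sex, region and sex by age group interaction term as factors and height at baseline as a covariate", with every term nested within week. It adds that "Conclusions from the primary analysis will be based on CIs for the specified treatment differences and not on hypothesis testing". Section 10.3.5 extends the model to one year: "Annualized HV at 13 weeks, 26 weeks, 39 weeks and 52 weeks will be analysed using a MMRM", again with baseline height as the only continuous covariate.

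The data for baseline HV are already required. Inclusion criterion 5 in section 6.1 restricts entry to a pre-treatment annualised HV below the 50th percentile, "calculated over a time span of minimum 6 months and maximum 18 months prior to screening". Section 9.4 states: "The pre-trial height assessment is collected to be used when evaluating inclusion criteria 5 and for baseline HV derivation". Height is also needed at screening for criterion 4 ("Impaired height defined as at least 2.5 standard deviations below the mean height for chronological age and gender at screening").

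The treatment of HV SDS differs. Section 10.3.2 models change in HV SDS, among other endpoints, with the baseline value of the analysed variable as covariate, and section 10.3.5 repeats this for week 52. So the plan derives a baseline velocity and adjusts for it in the supportive SDS analyses, but not in the cm/year analyses, one of which is primary. No reason is given.

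**The concern.** The baseline value of an outcome is a natural candidate covariate, and here it costs no extra data. Section 10.1 expects about 11 evaluable children per arm, and section 10.3.1 draws its conclusions from confidence intervals, so precision matters. Randomisation is not stratified on pre-treatment growth, so chance imbalance in it is possible with arms of this size. Adjustment would reduce the effect of such imbalance, though not remove it. What is at stake is some CI width, not the validity of the comparison.

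**Working it through.** **The plan's own figure.** Section 10.1 gives 11 per arm, SD 2.6 cm/year and a true difference of 3.25 cm/year; section 10.3 gives a two-sided 5% level. The standard error is 2.6 × √(2/11) = 1.109, so the noncentrality is 3.25/1.109 = 2.93. A two-sample t-test on 20 df then has power 79.6%, which matches the stated 80%. All nine cells of the power table reproduce within 0.6 percentage points.

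**Half-width as planned** (single time point, complete week-26 data, 2.6 taken as the residual SD). Parameters: intercept 1, treatment 4, and age group, sex, region, sex by age group and height 1 each, giving 10. Error df = 55 - 10 = 45. Half-width = t(0.975, 45) × 1.109 = 2.233 cm/year.

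**Half-width with baseline HV.** Let r be the partial correlation of baseline HV with week-26 HV, given the planned terms. One df is lost, and √(1 + 1/44) allows for chance imbalance in the new covariate:

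half-width = t(0.975, 44) × 1.109 × √(1 - r²) × √(1 + 1/44) = 2.260 × √(1 - r²).

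Break-even is where √(1 - r²) = 2.233/2.260, which on unrounded values gives r = 0.153.

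The formula gives averages. A simulation shows the spread across individual intervals: 5 × 11 children, the same model terms, independent covariates, an assumed 20% Japanese share, the four contrasts of section 10.3.1, and 6,000 runs per r.

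| r (assumed) | Half-width, cm/year | Average change in width | 95th percentile, one contrast | 95th percentile, worst of four | Share of CIs that widen |
|---|---|---|---|---|---|
| 0 | 2.260 | +1.2% | +4.9% | +7.5% | 81% |
| 0.1 | 2.248 | +0.7% | +4.7% | +7.2% | 72% |
| 0.2 | 2.214 | -0.9% | +4.1% | +6.7% | 50% |
| 0.3 | 2.155 | -3.5% | +2.8% | +5.3% | 26% |
| 0.4 | 2.071 | -7.3% | +1.2% | +3.3% | 10% |
| 0.5 | 1.957 | -12.4% | -1.7% | +0.2% | 2% |

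The first three columns come from the formula and the last three from the simulation. Simulated mean changes agree with the formula to within 0.4 percentage points. At r = 0, a Japanese share of 10% or 40% leaves the mean at +1.2%.

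**What the documents suggest about r.** They give no value, but several features point to a modest one:
- Criterion 5 cuts off the upper half of the HV distribution.
- The span varies from 6 to 18 months.
- The pre-trial height precedes the trial's own measurement procedure, in which height is taken "by a trained person blinded to treatment allocation (preferably the same person throughout the trial").
- At the lowest entry age of 2 years 26 weeks, an 18-month span puts the pre-trial height at about 2.5 - 1.5 = 1.0 year of age.
- Age group, sex and baseline height are already in the model.

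**The case against.** The strongest objection is that this is a preference without a demonstrated benefit. Randomisation protects the four contrasts without the covariate, and the choice of prognostic covariates beyond the stratification factors is a matter of judgement. The HV SDS models also already do much of the work. With the baseline value as covariate, a model for change gives the same treatment contrasts as a model for the on-treatment value, so the plan already delivers comparisons of velocity adjusted for baseline velocity at weeks 26 and 52. At r = 0.2 the average gain is under 1% and half of the individual intervals widen. A further run of 3,000 simulated trials found at least one of the four intervals widening in about 63% of trials at r = 0.2 and 39% at r = 0.3. Section 5.5 rests the extension II dose on the overall evidence of the main period, so no rule turns on CI width.

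Most of this stands, and it is why the point is optional. The SDS analyses partly cover the imbalance concern, but they are supportive and in other units, and they do not change the primary estimate in cm/year. They also show that baseline velocity must be derived in any case. An unknown r does not defeat a change whose average cost is capped near 1.2%.

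A reader might go further and infer that leaving out baseline HV biases the primary comparison, undermines the sample size, or leaves pre-treatment growth unaddressed. The documents support none of these. Allocation is randomised, the power figures reproduce from the stated SD without this covariate, and the SDS models adjust for it.

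**Conclusion.** The point holds as an optional improvement. Both cm/year HV models omit a baseline value that the plan collects for and must derive. The expected benefit is uncertain and probably modest: a change in average CI width from +1.2% (r = 0) through -0.9% (0.2) and -3.5% (0.3) to -12.4% (0.5). If 2.6 cm/year is the residual SD, that is a half-width moving from 2.23 to somewhere between 2.26 and 1.96 cm/year. The gain of about 12% needs r = 0.5, which nothing in the documents supports.

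The figures rest on an assumed r, 11 complete children per arm, and a single-time-point ANCOVA approximation to the MMRM. The percentage changes do not depend on the SD. Section 10.3.1 sets no margin and section 10.3 describes the trial as exploratory, so no documented threshold depends on this.

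**What to change.** If adopted, specify before the main-trial database lock:

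1. Add baseline HV (cm/year), nested within week, alongside baseline height in the HV MMRMs of sections 10.3.1 and 10.3.5.
2. Derive it from the same two heights and dates as baseline HV SDS, and write that derivation down once. Section 9.4 names the pre-trial height but not the second height; fixing the pair prevents two definitions of baseline velocity.
3. Mean-impute the covariate if it is missing, so that no child in the full analysis set is dropped. This should be rare, since criterion 5 needs the pre-trial height.

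If the sponsor prefers the present model, a one-line reason for leaving baseline HV out would be enough.

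The cost is a text change to two model descriptions, one derivation line and one missing-covariate rule; no new data are needed. The statistical price is one degree of freedom per week. If baseline HV is uninformative, intervals are about 1.2% wider on average, and about 5% wider at the 95th percentile for a single contrast (2.23 to about 2.34 cm/year). With 2 of 55 values mean-imputed these figures are essentially unchanged. Timing matters because adding the covariate after results are known would look data-driven.
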